13.3. Methods for Analysis

Data will be summarized with respect to baseline characteristics and safety measurements using descriptive statistics (quantitative data) and contingency tables (qualitative data). The safety analysis will consist of AE summaries (frequency tables based on CTCAE grades) and laboratory abnormalities summary. For the primary endpoint, the response rate and its 95% confidence interval will be estimated with a binomial distribution. Univariate and multivariate logistic regression model will be used to assess the association between response and several radiotherapy variables (biologic effective dose,

number of lesions treated, sequence of radiation and immune therapy), tumor variables (irradiated tumor site, size, growth rate, histology, PD-L1 status, local response, extent of prior chemotherapy use, and biologic correlates), and patient variables (age, smoking status, and other factors associated with secondary immunodeficiency). A predictive nomogram for response will be developed based on the outcome of the multivariate analysis. In the data analysis on the secondary endpoints, the Kaplan-Meier method will be used to estimate overall survival and progression-free survival. Wilcoxon signed-rank test for paired data will be used to assess the change of quality of life scores between two visits. Since the lung cancer score (LCS) of the FACT-L focuses on lung cancer symptoms, this will be used for the primary QOL endpoint; however, the more general subscales of physical and functional well-being on the Trial Outcome Index (FACT-TOI) will also be collected. A difference of 3 LCS points will be considered clinically significant.¹²⁻¹³ Where applicable, comparison will be made to previous randomized trials assessing immune checkpoint inhibitors alone in a comparable patient population.

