1.2. Secondary Objective(s)

To determine 1-year progression-free survival (PFS); 1-year overall survival (OS); safety/toxicity using CTCAE v4.0 until 30 days after the last dose of immune therapy or until the patient begins a new cancer-directed therapy, or death, whichever comes first; quality of life using FACT-L and FACIT Fatigue Scale at 3 month intervals until the time of systemic disease progression. In order to determine factors predictive of response to therapy, we will correlate the presence of response with radiotherapy variables (biologic effective dose, number of fractions, duration of radiotherapy, sequence of radiation and immune therapy), tumor variables (irradiated tumor site, size, histology, PD-L1 status, local response, extent of prior chemotherapy use), and patient variables (age, smoking status, and biologic correlates).

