3.4. Duration of Follow-Up

Follow-up of subjects should continue for 30 days after systemic disease progression or initiation of an alternate systemic therapy (whichever comes first). After the study period, the sponsor-investigator may still obtain data from a subject's medical records or by phone call in order to document overall survival per patient agreement. Any adverse events experienced after a patient has discontinued the study treatment will be followed until resolution, stabilization, or until it has been determined that the study treatment or participation is not the cause. Serious adverse events that are still ongoing at the end of the study period will necessitate follow-up to determine the final outcome. Any serious adverse event that occurs after the study period and is considered to be possibly related to the study treatment or study participation will be recorded and reported immediately.

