7.2. Adverse Event Evaluation

The investigator or designee is responsible for ensuring that all adverse events (both serious and non-serious) observed by the clinical team or reported by the subject which occur after the subject has started immune therapy are fully recorded in the subject’s medical records. Source documentation must be available to support all adverse events. A laboratory test abnormality considered clinically relevant (e.g., causing the subject to withdraw from the study, requiring treatment or causing apparent clinical manifestations, result in a delay or dose modification of study treatment, or judged relevant by the investigator), should be reported as an adverse event.

The investigator or sub-investigator (treating physician if applicable) will provide the following for all adverse events (both serious and non-serious):

- Event term (as per CTCAE version 4.0)
- Description of the event

- Date of onset and resolution
- **Expectedness of the toxicity**
- **Grade of toxicity**
- **Attribution of relatedness to the investigational agent- (this must be assigned by an investigator, sub-investigator, or treating physician)**
- Action taken as a result of the event, including but not limited to; no changes, dose interrupted, reduced, discontinued, etc. or action taken with regard to the event, i.e. no action, received con-med or other intervention, etc.
- Outcome of event

The most common adverse event from the short courses of focal radiation therapy used in this study will be fatigue. This may be accompanied by decreased appetite, changes in taste, or weight loss. Since radiation is a focal, localized treatment to a specific targeted tumor, the likelihood of all other side effects is dependent on the part of the body that is treated, as described in the table below. Unknown side effects may also arise due to the combination of radiation therapy and immunotherapy in this study.

	Acute/Short-Term/Temporary	Chronic/Long-Term/Permanent
Skin	redness, dryness, darkening, itching, peeling, tenderness, hair loss	thickening, firmness, discoloration, hair loss
Bone	decreased blood counts	fracture, pain
Nerves	electrical sensation	pain, loss of strength, numbness, tingling, paralysis
Lymphatics	Swelling	lymphedema
Brain	fatigue, brain swelling, headaches, nausea, vomiting, dizziness, drowsiness, altered taste or smell	loss of strength, numbness, tingling, paralysis

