7.3. Adverse Event Reporting Procedures

All patients will be evaluable for toxicity from the time of their first treatment with immune therapy. It is the responsibility of all investigators to assess AEs during the subject's participation in the study. Subjects will be followed for **30** days after treatment has stopped or until an alternative systemic therapy has been started or until death, whichever comes first. Each AE should be followed until resolution, stabilization, or until it has been determined that the study treatment or participation is not the cause.

Adverse events that occur after the subject has started immune therapy must be documented in the study database/case report forms (OnCore or other PRMC approved database), subject's medical records, and as required per additional institutional standards. Source documentation must be available to support all reported adverse events.

A laboratory test abnormality considered clinically relevant (e.g., causing the subject to withdraw from the study), requiring treatment or causing apparent clinical manifestations, or judged relevant by the investigator, should be reported as an adverse event.

This protocol will use the NCI Common Terminology Criteria for Adverse Events (CTCAE) version 4.0 available at <http://ctep.cancer.gov> for adverse event reporting.

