⁶Serum chemistries include sodium, potassium, chloride, bicarbonate, BUN, creatinine, glucose, calcium, magnesium, phosphorous, albumin

⁷Serum liver function tests include alkaline phosphatase, total bilirubin, total protein, SGOT [AST], SGPT [ALT]

⁸Only for women of childbearing potential (within 14 days of registration)

⁹Only for patients with diabetes mellitus

¹⁰In patients with contrast allergy a short course of steroids may be given as needed. In patients with poor kidney function in whom contrast is contraindicated a non-contrast imaging study is permissible.

¹¹Please refer to protocol section 9 for details. The initial research blood sample may be drawn anytime between signing the consent and the first immune therapy treatment.

¹²Record all past and current administrations of immune therapy (sections 5.2 and 6.2), including date and dose of each administration.

¹³Record all past and current administrations of radiation therapy (sections 5.1, 5.3, and 6.1), including for each course: the start and end date, total dose, dose per fraction, number of fractions, and location of treated lesion.

¹⁴Survival assessment may be carried out via chart review or phone call only.

¹⁵A window of \pm 14 days around the standard time point every 3 months is allowed as necessary

¹⁶A minimum of one scan every 4 months is required, however, scans may be completed at more frequent intervals as clinically indicated.

¹⁷Performed in coordination with imaging studies, at baseline prior to treatment, and thereafter only for a change in extracranial response on follow-up imaging. The blood will be drawn within 30 days of any imaging study showing a change in extracranial response status.

¹⁸Optional rebiopsy of an accessible non-irradiated tumor may be obtained at the treating physicians' discretion if it is deemed clinically warranted and safe to perform, for diagnostic purpose in order to confirm progression of disease and underlying histopathology. If indicated, it should be carried out within 30 days of the confirmatory imaging study showing disease progression, and prior to initiating any further systemic therapy.

¹⁹AEs and SAEs will be collected on a continuous basis starting with the first cycle of immune therapy. Both AEs and SAEs will be collected up until 30 days after the last dose of immune therapy or until the patient begins a new cancer-directed therapy, or death, whichever comes first.

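### AE collection follows time on immune therapy and Section 13.3 plans only crude frequency tables, so late, mainly non-serious, radiation toxicity will be understated by an amount the documents do not fix

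*Combined protocol and SAP*

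**What the plan says.** - **Analysis.** Section 13.3: "The safety analysis will consist of AE summaries (frequency tables based on CTCAE grades) and laboratory abnormalities summary". Kaplan-Meier estimation is planned there for overall and progression-free survival only. Section 7.3 makes every patient evaluable for toxicity from the first immune therapy dose.
- **Collection window.** Section 10.2, footnote 19: "Both AEs and SAEs will be collected up until 30 days after the last dose of immune therapy", or to new cancer-directed therapy or death if earlier. Section 1.2 agrees: "safety/toxicity using CTCAE v4.0 until 30 days after the last dose of immune therapy".
- **Other wordings.** Section 7.3 follows patients for 30 "days after treatment has stopped or until an alternative systemic therapy has been started or until death, whichever comes first", without saying which treatment is meant. Section 3.4 uses another anchor: "Follow-up of subjects should continue for 30 days after systemic disease progression or initiation of an alternate systemic therapy".
- **After the window.** The calendar column for the time after progression or switch marks survival and an optional rebiopsy, but no AE assessment. Section 3.4 keeps one route open: "Any serious adverse event that occurs after the study period and is considered to be possibly related to the study treatment or study participation" is still recorded and reported.
- **What ends immune therapy.** Section 5.2: progression or unacceptable toxicity. Section 3.3 allows it to continue past progression.
- **Radiation.** Section 7.2 lists, by organ, effects under "Chronic/Long-Term/Permanent". Section 5.3 allows a stand-alone final course up to 6 weeks after immune therapy stops.

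**The concern.** Radiation is the experimental component (Section 6.2 says immune therapy is not), yet the AE clock runs on the drug. A patient who progresses early and stops is observed for a short time after radiation. A patient with a lasting response may be observed for a year or more. Late effects such as fracture, stricture, fistula or loss of lung capacity need time to appear, and a frequency table takes no account of how long each patient was observed.

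The late-toxicity percentage therefore falls simply because patients stop the drug. Safety of the combination is part of the overall objective in Section 1, and toxicity is a secondary endpoint. A low tabulated rate could be read as good tolerability when it partly reflects short observation.

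**Working it through.** The documents give no late-toxicity rate, time on therapy, survival after stopping or onset time, so there is no figure of the plan's own to reproduce. The inputs below are assumptions except where a section is named. Start of new therapy, which would shorten the window further, is left out.

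**1. Death ignored.** Let time on immune therapy be exponential with median m months, and k = ln 2 / m. With the one-month tail, the share still under AE collection at month t is exp(−k(t − 1)). If late events arise evenly over months 3 to 12, the share falling inside the window is [exp(−2k) − exp(−11k)] / (9k).

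| m (months) | Under collection, month 6 | Month 12 | Late events inside window | Lost |
|---|---|---|---|---|
| 3 | 31% | 8% | 0.265 | 74% |
| 4 | 42% | 15% | 0.358 | 64% |
| 6 | 56% | 28% | 0.494 | 51% |

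**2. Death counted.** Step 1 counts as lost some events in patients who would have died first. The proper comparison is with follow-up to death:

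loss = 1 − P(onset before the earlier of end of collection and death) / P(onset before death).

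Worked case: m = 6, median survival after stopping 3 months, onset even over months 3 to 12. Let a = ln 2 / 6 and b = ln 2 / 3, so b = 2a.
- Mean of exp(−at) over months 3 to 12: (0.7071 − 0.2500) / 1.0397 = 0.4397. Mean of exp(−bt): (0.5000 − 0.0625) / 2.0794 = 0.2104.
- Onset before death: 2 × 0.4397 − 0.2104 = 0.669.
- Onset before death and inside the window: 0.4397 × [1 + (1 − exp(−0.1155))] = 0.4397 × 1.1091 = 0.488.
- Loss: 1 − 0.488 / 0.669 = 27%, against 51% with death ignored.

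With median survival after stopping of 3 to 12 months and the same onset, the loss is 49–67% (m = 3), 39–57% (m = 4) and 27–44% (m = 6).

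**3. Responder mixture, death counted.** Responders are 20% or 40% of patients (the design rates in Section 13.2). They stay on therapy for 2 months plus an exponential time with median 14 months, within the 12.5–17.0 months of Section 2.2. Non-responders have a median of 2, 3 or 4 months on therapy. Median survival after stopping is 3, 6 or 9 months. Onset is even over months 3–12, 6–12 or 6–24.
- Loss by simulation: **24%** (40% responders, 4 months, survival 3 months, onset 3–12) to **73%** (20% responders, 2 months, survival 9 months, onset 6–24).
- A true 10% late risk would be tabulated as 10 × (1 − 0.73) = 2.7% to 10 × (1 − 0.24) = 7.6%.
- With death ignored and responder medians of 12.5 or 17 months, the range is 45–87%.
- These scenarios imply one-year survival of 27–72%, above the 15–20% in Section 2.1. For a given time on therapy, poorer survival makes the loss smaller.

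**4. Wider sensitivity.** A single exponential with median 2 to 12 months, over all three onset windows and with death counted, gives 14–95%. The direction never changes.

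**5. Final radiation course against the window.** Days of AE window left when the course starts d days after the last immune therapy dose are 30 − d: 30 at d = 0, 16 at d = 14, 0 at d = 30, and −12 at d = 42 (6 weeks). A permitted course can start 12 days after collection under footnote 19 has ended, so even its acute toxicity falls outside.

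**The case against.** The strongest reply is that collection does not simply stop at footnote 19. Section 3.4 records possibly related serious events after the study period without a time limit, and follows AEs arising after discontinuation to resolution or stabilization. Several listed late effects, such as perforation, fistula and paralysis, could meet the serious-event definition in Section 7.1.2. This stands in part: the worst events are the least likely to be lost. But no scheduled assessment supports that route, and new non-serious events outside the window are not clearly covered.

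It can also be said that toxicity is a secondary, descriptive endpoint and that re-analysis recovers no missed event. Both are true. On the figures in step 1, about 33 × 0.08 = 3 to 33 × 0.28 = 9 patients would still be under collection at month 12, so any late estimate will be imprecise. The added analysis stops unobserved patients from counting as event-free; only an aligned window recovers events.

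Three stronger readings are tempting, and the documents do not support them:
- *That half to three quarters of late events are certainly lost.* This follows from step 1, which ignores death and rests on assumed times. With death counted, the lower end falls to about a quarter.
- *That late toxicity is looked for mainly in responders.* Under footnote 19 progression alone does not close the window, and Section 3.3 allows drug past progression. In the mixture with death ignored, responders supply 35–94% of late observation time, so this often holds but not always.
- *That comparison with published trials favours the combination by construction.* Section 13.3 says "Where applicable, comparison will be made to previous randomized trials assessing immune checkpoint inhibitors alone in a comparable patient population". That sentence does not name toxicity, and those trials' AE windows are not in the documents.

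**Conclusion.** The point holds in direction. Observation time depends on outcome, the planned summary ignores it, and late radiation toxicity, mainly non-serious, will be understated. A loss of roughly a quarter to three quarters is a reasonable working range. It rests on assumed time on therapy, survival after stopping and onset, with death competing; more extreme inputs give 14–95%. For serious events the loss is smaller by an amount that cannot be computed.

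Two further points need no assumptions. Sections 1.2 and 10.2, 3.4 and 7.3 do not state one AE window, and Section 5.3 permits a final radiation course that starts after the footnote 19 window has closed.

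**What to change.** In Section 13.3, keep the frequency tables and add, for radiation-attributed AEs:

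1. **Acute events**, within a stated period of the most recent course to the treated site, as frequencies among treated patients. The protocol gives no cut-off, so the sponsor must state one.
2. **Late events**, after that period on the same site-specific clock, as cumulative incidence with death competing and censoring at the end of AE collection. State the time origin, and show the number at risk and the total time under observation. Say plainly that the censoring is informative, because it follows progression and toxicity.

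Using one clock for both labels matters. Section 5.3 foresees courses about 2 months apart, so a late period counted from the first course would overlap an acute period counted from each course.

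Separately, reconcile the AE windows in Sections 1.2, 3.4, 7.3 and 10.2 with the final-course provision in Section 5.3, so that there is a single tabulated risk period and it covers every radiation course.

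Cost: the analysis needs onset dates and radiation dates that are already collected, and a little more work. A window that covers every course may add some AE follow-up after immune therapy ends. The late estimates will look less favourable and, with 33 patients, will carry wide intervals.

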13.2. Sample Size/Accrual Rate

The primary analysis will be for patients enrolled at time-points (A) and (B) above, whereas patients enrolled at time-point (C) will be included in observational analysis only (see section 3.1). The primary endpoint of this study is the overall response rate (complete + partial response) and the efficacy will be assessed using the Simon's two-stage Minmax design. A sample size of 33 patients is chosen to differentiate between the response rate of 20% and 40% with 80% power at a significance level of 0.05. In particular, 18 patients will be enrolled at the first stage. If 15 or more of the first 18 patients have disease progression prior to any response, the trial will be terminated; otherwise an additional 15 patients will be treated for a total of 33 patients. In the final data analysis, if 10 or fewer patients respond among 33 patients, the treatment will be concluded ineffective. The probability of early termination due to futility is 0.72.

For correlative study between biomarkers and response, this sample size will have at least 80% power to detect a 50% change/difference on biomarker data between response and non-response groups using a two-sided two-sample t-test at 0.05 significance level, assuming that the response rate is 35% or higher and the coefficient of variation (CV) of biomarkers is 0.45.

Approximately 100 patients with metastatic NSCLC are diagnosed and treated each year at our institution, many of whom will be candidates for immune checkpoint therapy. As such, we expect to accrue 3 patients per month to this trial for an estimated accrual period of one year. The full estimated duration of the study is two years.

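### The 95% binomial interval planned in 13.3 is not aligned with the one-sided two-stage count rule in 13.2, and no estimate allows for the stage-1 stop

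*Combined protocol and SAP*

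**What the plan says.** Section 13.2 (Sample Size/Accrual Rate) states that "the efficacy will be assessed using the Simon's two-stage Minmax design". The design compares 20% with 40% "with 80% power at a significance level of 0.05"; whether that level is one- or two-sided is not said. At stage 1, "18 patients will be enrolled at the first stage", and the trial stops if at least 15 of them progress without a preceding response. The probability of stopping for futility is given as 0.72. The final rule is: "In the final data analysis, if 10 or fewer patients respond among 33 patients, the treatment will be concluded ineffective". By implication, 11 or more is a favourable result, although the section never puts it in those words.

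Section 13.3 (Methods for Analysis) says for the primary endpoint that "the response rate and its 95% confidence interval will be estimated with a binomial distribution". It does not name the type of interval (exact, Wilson or other). It does not mention the two-stage design, and it does not say how the interval is to be read beside the cut-off.

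**The concern.** A test and an interval reported for the same endpoint usually tell the same story. Here the test spends about 5% in one tail and the interval 2.5% in each. The interval also treats the final count as a plain binomial, although trials with few early responses never reach 33 patients. At the smallest passing count the report could therefore say that the rule was met and, in the next line, show an interval that contains 20%.

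This matters because section 13.3 also plans comparison with earlier checkpoint-inhibitor trials, whose response rates section 2.2 gives as 19-25%. Readers will set the reported rate and interval against figures close to the null. With no prior statement of which summary governs, the emphasis could be chosen after a borderline result is seen.

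**Working it through.** **Inputs.** From 13.2: p0 = 0.20, p1 = 0.40, n1 = 18, n = 33 (15 in stage 2), final cut-off r = 10, stated early termination 0.72. From 13.3: 95% binomial interval. The stage-1 response cut-off r1 is not stated as a response count. If every patient who does not respond counts as progressing, 15 or more of 18 means r1 = 3. The stated 0.72 is checked against this first. All 33 patients are assumed to be in the denominator.

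**1. Reproduce the design.** With X1 ~ Bin(18, p) and X2 ~ Bin(15, p):

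- early termination = P(X1 ≤ r1)
- rejection = Σ over x > r1 of P(X1 = x) · P(X2 ≥ 11 − x)

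| r1 | early termination at 20% | one-sided alpha | power at 40% |
|---|---|---|---|
| 4 | 0.716 | 0.0458 | 0.801 |
| 3 | 0.501 | 0.0497 | 0.825 |

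Only r1 = 4 gives 0.72. A full search confirms that 33 is the smallest total for one-sided alpha ≤ 0.05 and power ≥ 0.80. A one-sided 0.025 level is not met under either boundary, so the rule is in effect one-sided at 5%.

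**2. Ordinary intervals at 11/33 = 33.3%.** The exact (Clopper-Pearson) 95% limits solve P(X ≥ 11) = 0.025 and P(X ≤ 11) = 0.025 for X ~ Bin(33, p), giving 0.180 to 0.518. The other 95% lower limits are Wilson 0.198, Agresti-Coull 0.197, Jeffreys 0.192 and Wald 0.172; all are below 0.20. At 12/33 the exact interval is 0.204 to 0.549 and excludes 20%. Only Wald (0.1995) still includes it there.

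**3. Level or stage adjustment?** The stagewise lower limit solves P(X1 > r1 and X1 + X2 ≥ 11) = a. The upper limit solves 1 − P(X1 > r1 and X1 + X2 ≥ 12) = a. With r1 = 4:

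- 95% (a = 0.025): 0.182 to 0.526, includes 20%
- 90% (a = 0.05): 0.203 to 0.497, excludes 20%
- ordinary exact 90%, for comparison: 0.1995 to 0.491, just includes 20%

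The confidence level does most of the work; the stage adjustment settles the margin. With r1 = 3 the stagewise 90% interval is 0.2002 to 0.492, which still agrees with the rule.

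**4. How often.** With r1 = 4, P(exactly 11/33 after passing stage 1) is 0.093 at a true 40%, 0.124 at 35% and 0.116 at 30%.

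**5. Bias of the naive rate.** Averaged over all trials, its mean is Σ over x ≤ r1 of (x/18)·P(X1 = x), plus the sum over x > r1 and all y of ((x + y)/33)·P(X1 = x)·P(X2 = y). With r1 = 4:

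- true 0.20: mean 0.185, bias −1.5 points
- true 0.30: mean 0.282, bias −1.8 points
- true 0.40: mean 0.391, bias −0.9 points

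**6. UMVUE at 11/33.** This is Σ C(17, x−1)·C(15, 11−x) divided by Σ C(18, x)·C(15, 11−x), for x from r1 + 1 to 11. With r1 = 4 it is 59,173,192 / 167,773,476 = 0.353. With r1 = 3 it is 63,548,992 / 187,464,576 = 0.339.

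**7. Coverage of the plain exact 95% interval under the two-stage design.** Coverage is the total probability of the outcomes whose interval contains p, using n = 18 for stopped trials and n = 33 otherwise. On a grid of true rates from 20% to 40% in steps of 0.25 points it is never below 0.95 under either boundary. Above 40% it dips to 0.946 (r1 = 4, near 48%) or 0.948 (r1 = 3, near 42%).

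**The case against.** A reader might infer that the two sections contradict each other. The documents do not support that. Section 13.2 decides on the count. Section 13.3 gives the interval an estimation role only, with no requirement to exclude 20% and no power to override the cut-off. A two-sided 95% interval is expected to be stricter than a one-sided 5% test, and reporting one beside a Simon rule is conventional. This objection stands.

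A reader might also infer that the trial really has power of only 0.71. That figure (0.709, one-sided alpha 0.0205) would apply only if the interval had to exclude 20%, so that 12/33 was needed. The plan makes no such demand.

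Nor does the planned interval fail as an interval: its coverage is at or essentially at 95%. The mismatch is confined to one outcome for every common method except Wald.

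The bias also has two sides. The downward bias is an average over all trials, including those that stop. Among trials that reach 33 patients (r1 = 4), the naive mean is above the truth: 0.264 at a true 0.20 and 0.332 at 0.30. The UMVUE mean there is higher still, 0.318 and 0.359. The UMVUE is therefore unbiased over the whole design but not a correction for trials that continue. These points justify adding the design-matched summary rather than replacing the planned one.

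**Conclusion.** The point holds as a misalignment that is worth a modest, inexpensive clarification. It does not change the efficacy decision, and it does not show a contradiction, a loss of power or an invalid interval.

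Its size is one borderline outcome, 11/33, with a probability of about 9% to 12% at true rates of 30-40%, and an average bias in the reported rate of under 2 points at the true rates of 20%, 30% and 40%.

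The conclusion rests on three assumptions: the test is one-sided, as the stated figures imply; all 33 patients are counted, although section 11.1.2 restricts who is evaluable for response; and stage 1 works as a response-count boundary. The size of the correction depends on that boundary: 35.3% against 33.9% for the UMVUE at 11/33. The agreement of the stagewise 90% interval with the rule holds for both boundaries, though with a boundary of 3 the lower limit clears 20% only barely, at 20.02%.

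**What to change.** 1. Before coding anything, reconcile the stage-1 text in 13.2 with the stated 0.72. As written, the rule corresponds to at most 3 responses (early termination 0.50); the stated probability corresponds to at most 4. The text also counts progression before response rather than non-response, so the boundary should be expressed as a number of responses.
2. State in 13.2 that the test is one-sided at 5%, and in 13.2 and 13.3 that the responder count decides.
3. In 13.3, keep the planned 95% interval and name its method. Add the UMVUE with a stagewise 90% interval, or the equivalent one-sided 95% lower limit, matched to the reconciled design. At 11/33 these would be 35.3% (20.3% to 49.7%) for a boundary of 4, or 33.9% (20.02% to 49.2%) for a boundary of 3.

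The cost is a few sentences and a few lines of code, with no extra patients or data. The downsides are a less familiar interval and a UMVUE that is somewhat more variable near 20%: with a boundary of 4, root mean squared error is 0.091 against 0.079 for the naive rate.
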